### Stable disease

 This is present when the subject fails to qualify either for a CR, partial remission, or progressive disease.

Date: 20 March 2019 Page 77 of 122

# Progressive disease

Product: Blinatumomab

 An increase of at least 25%, or an absolute increase of at least 5,000 cells/µL (whichever is greater), in the number of circulating leukemia cells, development of extramedullary disease, or other laboratory or clinical evidence of progressive disease.

Relapse is defined by the following criteria:

Hematological relapse:

 Proportion of blasts in bone marrow > 25% or extra medullary relapse following documented CR

## MRD relapse

Increase of MRD level by at least 1 log following an MRD response

# 7.2.11 Laboratory Assessments

The analytes for all laboratory tests used throughout this study are listed in the table below. All screening and on-study laboratory samples will be collected and processed at the investigator's local laboratory and analyzed locally or centrally. Chemistry, creatinine clearance, coagulation tests, hematology, urinalysis, IgG and pregnancy confirmation will be performed locally. Anti-blinatumomab antibody and HAMA samples, PK samples, cytokines, lymphocyte subsets, as well as bone marrow samples for hematological and MRD assessments will be evaluated centrally. Cytokines, lymphocyte subsets, and PK samples are not required for the expansion cohort.

Amgen or the central laboratories will supply containers for sample collection, preparation, packaging, and shipping. Detailed instructions for sample collection, processing, and shipping are provided in the central laboratory manual and/or Amgen-provided training materials. The date and time of sample collection will be recorded in the source documents at the site.

Blood draws should not be done via the central venous access. Exception: If a permanent central line with more than one lumen is used, blood draws can be done via the lumen that is not used for drug administration.

The below Table 8 outlines the specific analytes that will be assessed during the study at time points outlined in the Schedule of Assessments (Table 6).

Protocol Number: 20130265 Page 78 of 122

**Product: Blinatumomab** Date: 20 March 2019

		~		
Local	Local	Local	Local	Other Labs
Laboratory	Laboratory	Laboratory	Laboratory	Local Laboratory
Chemistry	Coagulation	Urinalysis a	Hematology	Hepatitis B surface
Sodium	aPTT/INR	Blood	Hemoglobin	antigen
Potassium		Protein	Hematocrit	Hepatitis B surface
Chloride		Glucose	Reticulocytes	antibody
Total protein			Platelets	Hepatitis B core
Albumin			WBC	antibody
Calcium			RBC	Hepatitis C virus
Magnesium			Differential	antibody
Phosphorus			
 
Neutrophils
 
	IgG
Glucose			
 
Bands/stabs
 
	Urine or serum
BUN or Urea			
 
Eosinophils
 
	pregnancy
Creatinine			
 
Basophils
 
	CSF analytes
Creatinine			
 
Lymphocytes
 
	
clearance			

Monocytes

	
Uric acid			Blasts	Central
Alk phos				Laboratory
LDH				Anti-blinatumomab
AST (SGOT)				antibodies
ALT (SGPT)				HAMA
C-reactive				
protein				Phase 1b/2 only:
Amylase b				PK c
Lipase b				Cytokines c
Bilirubin (total)				Lymphocyte
GGT				subsets c

<sup>a The presence of glucose, protein and blood in urine will be assessed by dipstick during baseline at D1 before the start of infusion at each cycle, and at the safety follow-up visit.

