### **Secondary Endpoints:**

- TTHR
- RFS
- Allogeneic HSCT (alloHSCT) treatment with blinatumomab
- Best overall response within 2 cycles of treatment with blinatumomab
- OS
- Incidence and severity of adverse events
- 100-day mortality after alloHSCT
- Blinatumomab PK parameters (eg, steady state concentration [Css] and clearance of blinatumomab)
- Serum cytokine concentrations
- Incidence of anti-blinatumomab antibody formation

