## 7.2.14 Pharmacokinetic Assessments

Pharmacokinetic testing is required for subjects participating in the Phase 1b/2 parts of the study. Pharmacokinetic testing is not required for subjects participating in the expansion cohort. Serum samples will be collected to measure blinatumomab serum concentration during the blinatumomab treatment period in all subjects who received the drug during the study. Samples will be collected at time points outlined in the Schedule of Assessments (Table 6) for determination of serum steady state drug concentrations  $(C_{ss})$ . The samples will be measured with a validated bioassay.

PK samples must be drawn from a site that is distal from the site where the investigational product has been administered to avoid contamination of the PK samples and to better estimate PK parameters. On PK assessment days, the date and time of infusion bag changes and any dosing interruptions will be recorded in the eCRF.

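### Protocol 7.2.11 allows blood draws through the spare lumen of the infusing central line without excepting PK samples, which 7.2.14 requires from a distal site

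*Protocol*

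**What the plan says.** Protocol Section 7.2.11 opens with a general scope: "All screening and on-study laboratory samples will be collected and processed at the investigator's local laboratory and analyzed locally or centrally". The same paragraph lists the samples evaluated centrally, beginning "Anti-blinatumomab antibody and HAMA samples, PK samples, cytokines, lymphocyte subsets, as well as bone marrow samples", and Table 8 in that section also lists PK. The section then sets a draw-site rule, "Blood draws should not be done via the central venous access", followed by one exception. Where a permanent central line has more than one lumen, "blood draws can be done via the lumen that is not used for drug administration". PK is not excepted, and there is no reference to 7.2.14.

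Protocol Section 7.2.14 has its own rule: "PK samples must be drawn from a site that is distal from the site where the investigational product has been administered to avoid contamination". It adds better estimation of PK parameters as a second reason. It does not define what counts as distal.

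On PK days, 7.2.14 has the eCRF record bag-change times and dosing interruptions, and 7.2.11 has the source documents record the date and time of collection. Neither mentions the draw site. SAP 10.8.1 provides for excluding values affected by dosing interruptions or administration errors.

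**The concern.** The exception in 7.2.11 presupposes that drug is running through another lumen of the same line. A second lumen of the infusing catheter is hard to read as a site distal from administration. One section therefore permits, for a PK sample, what another section rules out. The risk is the one 7.2.14 itself names: infusate reaching the sample.

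Css and clearance are named secondary endpoints in Phase 1b and Phase 2. Protocol 2.1.4 reports only 5 Asian subjects with evaluable PK samples from the earlier adult studies, so this trial adds materially to that evidence. Phase 1b has at most 6 evaluable subjects per dose level (Protocol 10.2.1), and SAP 10.8.1 summarizes PK by dose, cycle and age group. One or two affected subjects could shift a summary. The Data Review Committee may look at PK data when selecting the Phase 2 dose, and exposure-response work may follow (SAP 10.8.3).

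**Working it through.** The plan states no figure on this point, so there is none to reproduce. The check has four parts.

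**1. The two rules compared.**

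| | Section 7.2.11 | Section 7.2.14 |
|---|---|---|
| Scope | All on-study laboratory samples, PK named | PK samples only |
| Force | Permissive (can) | Mandatory (must) |
| Spare lumen of the infusing line | Allowed | Not a distal site on a natural reading |
| Reference to the other section | None | None |

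A draw at a distal site satisfies both rules. A draw through the spare lumen satisfies 7.2.11 only. The PK timing instructions in Table 6 (footnote h) and Section 7.2.3 give no draw-site rule and do not point to 7.2.14.

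**2. Samples taken while drug is infusing** (Table 6, footnote h, cycle 1).

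- Adults: day 1 pre-dose, +2h, +6h, +10h; day 2 +24h; day 8 0h; day 15; day 29 0h and +1h, +2h, +4h, +6h after the end of infusion. Total 4 + 1 + 1 + 1 + 5 = 12. Removing 1 pre-dose and 4 post-infusion samples leaves 7 of 12 (58%).
- Pediatric: day 1 pre-dose, +2h, +10h; day 2 +24h; day 15; day 29 0h and +2h, +6h after the end of infusion. Total 3 + 1 + 1 + 3 = 8. Removing 1 pre-dose and 2 post-infusion samples leaves 5 of 8 (63%).
- The steady-state samples (adult day 8, day 15 and day 29 0h; pediatric day 15 and day 29 0h) are all taken during infusion, as are all later-cycle samples.

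**3. Direction.** Let f be the volume fraction of infusate in the sample, R0 the infusion rate and V the daily infusion volume. Then observed Css = (1 − f) × Css + f × R0/V, and clearance = R0/Css. The error in Css is f × (R0/V − Css), which is positive whenever infusate is more concentrated than serum. Css is overstated and clearance understated.

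**4. Scale, for illustration only.** R0 = 28 µg/day is from Protocol 6.2.2.3. Assumed, and not in the documents: V = 60 to 240 mL/day, true Css = 200 to 1,000 pg/mL, and the values of f. Infusate concentration is 28,000,000 pg ÷ 240 mL = 116,667 pg/mL up to 28,000,000 pg ÷ 60 mL = 466,667 pg/mL.

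| f | Observed ÷ true Css | Observed ÷ true clearance |
|---|---|---|
| 0.01% | 1.01 to 1.23 | 0.99 to 0.81 |
| 0.1% | 1.12 to 3.33 | 0.90 to 0.30 |

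Example at f = 0.1%, V = 60, Css = 200: 0.999 × 200 + 0.001 × 466,667 = 666.5 pg/mL, and 666.5/200 = 3.33.

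**The case against.** The strongest reply is that the rules do not truly collide. Section 7.2.11 starts from a prohibition, and its exception is narrow and permissive. Section 7.2.14 is specific to PK and mandatory. No passage requires a PK draw through the line, so a site can always comply with both. This stands: 7.2.14 should govern, and contamination can arise only where a site acts on 7.2.11 alone.

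The analysis also has a route for affected data. Protocol 10.1.2.5 and SAP 7.6 allow PK evaluation to be withheld for significant protocol deviations or missing key sampling information, and SAP 9.5 has suspected outliers investigated. This stands in part. A draw that 7.2.11 expressly permits may never be logged as a deviation, and a modest upward shift need not look like an outlier.

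Protocol 7.2.11 also defers detailed collection instructions to the central laboratory manual and training materials, which are not available here. They may settle the draw site, so one cannot say that the instruction is absent from the trial, only that the protocol text does not give it.

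A reader might also infer that almost all PK draws occur during infusion. The schedule does not show that: in cycle 1, 5 of 12 adult and 3 of 8 pediatric samples fall before or after the infusion.

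**Conclusion.** The two sections need to be reconciled. Section 7.2.11 gives a permission, without a PK exception, that is at odds with the PK requirement in 7.2.14, and the documents shown do not name the draw site as a recorded item. If a site relied on that permission, any carry-over would bias Css upward and clearance downward.

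The size is unknown. Infusion volume, true Css and carry-over fraction in the illustration are all assumed, and nothing in the documents supports a particular amount of carry-over between lumens. A reader might infer that the trial's Css and clearance estimates are wrong. The documents do not support that: they show a route to contamination, not that any sample was taken that way.

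The reach is limited to the descriptive secondary PK endpoints and any exposure-response analysis built on them. DLT, CR/CRh* and the two-stage Phase 2 design are untouched, and the expansion cohort has no PK sampling.

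**What to change.** - **Protocol 7.2.11:** add one sentence stating that the multi-lumen exception does not apply to PK samples, which follow 7.2.14.
- **SAP 10.8.1:** add a sentence that concentrations known from source records to have been drawn through the infusing catheter will be flagged, and excluded in a sensitivity summary of Css and clearance.

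The cost is one sentence in each document, plus a check of source records. Subjects carry no new burden, because 7.2.14 already requires distal draws. The SAP version history already refers to the report of the primary analysis, so many or all of the PK samples may predate these versions. In that case the protocol sentence comes late, while the SAP step can still be used, as far as sites recorded the draw site.

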#### 7.2.12 **Lymphocyte Subsets**

Lymphocyte subset testing is required for subjects participating in the Phase 1b/2 parts of the study. Lymphocyte subset testing is not required for subjects participating in the expansion cohort. Lymphocyte subsets will be measured by flow cytometric determination of different markers (eg, T cells: CD3, CD4, CD8; B cells: CD19; T cell subsets: CD45RA, CD197, and others). Lymphocyte subsets will be collected at time points outlined in the Schedule of Assessments (Table 6).

If B-cell counts have not recovered at the safety follow-up visit (recovered is defined as number of CD19-positive cells per µL is 90 to 570) (McNerlan et al, 1999), and the subject has not relapsed, another sample will also be taken 6 months after SFU visit for determination of lymphocyte subsets.

<sup>b At screening only.

<sup>c Not required for subjects enrolled in the expansion cohort.

Product: Blinatumomab Protocol Number: 20130265

Date: 20 March 2019 Page 79 of 122

# 7.2.13 Immunoglobulins

Immunoglobulins (IgG only) will be collected at time points outlined in the Schedule of Assessments (Table 6) to detect hypogammaglobulinemia or immunological changes.

## 7.2.14 Pharmacokinetic Assessments

Pharmacokinetic testing is required for subjects participating in the Phase 1b/2 parts of the study. Pharmacokinetic testing is not required for subjects participating in the expansion cohort. Serum samples will be collected to measure blinatumomab serum concentration during the blinatumomab treatment period in all subjects who received the drug during the study. Samples will be collected at time points outlined in the Schedule of Assessments (Table 6) for determination of serum steady state drug concentrations  $(C_{ss})$ . The samples will be measured with a validated bioassay.

PK samples must be drawn from a site that is distal from the site where the investigational product has been administered to avoid contamination of the PK samples and to better estimate PK parameters. On PK assessment days, the date and time of infusion bag changes and any dosing interruptions will be recorded in the eCRF.

# 7.3 Antibody Testing Procedures

Blood sample(s) will be collected at timepoints as outlined in the Schedule of Assessments (Table 6) for the measurement of anti-blinatumomab binding antibodies. Samples testing positive for binding antibodies will also be tested for neutralizing antibodies and may be further characterized for quantity/titer, isotype, affinity and presence of immune complexes. Additional blood samples may be obtained to rule out anti-blinatumomab antibodies (ADA) during the study.

Sites will be notified of any positive neutralizing antibody results to blinatumomab for individual subjects at the end of the study for each subject. If results are not provided, no neutralizing antibodies to blinatumomab have been detected.

Subjects who test positive for neutralizing antibodies to blinatumomab at the End of Safety Follow up visit may be asked to return for additional follow-up testing. This testing is to occur approximately every 3 months starting from when the site has been notified of the positive result, until: (1) neutralizing antibodies are no longer detectable or (2) the subject completed Follow up period for the study. All follow-up results, both positive and negative will be communicated to the sites. More frequent testing (eg, every month) or testing for a longer period of time may be requested in the event of

Date: 20 March 2019 Page 80 of 122

safety-related concerns. Follow-up testing is not required where it is established that the subject did not receive blinatumomab.

Subjects who test positive for binding, non-neutralizing antibodies and have clinical sequelae that are considered potentially related to an anti-blinatumomab antibody response may also be asked to return for additional follow-up testing.

# 7.4 Biomarker Development

Biomarker analyses are not planned for this study.

# 7.5 Sample Storage and Destruction

Any blood sample (eg, PK) collected according to the Schedule of Assessments (Table 6) can be analyzed for any of the tests outlined in the protocol and for any tests necessary to minimize risks to study subjects. This includes testing to ensure analytical methods produce reliable and valid data throughout the course of the study. This can also include, but is not limited to, investigation of unexpected results, incurred sample reanalysis, and analyses for method transfer and comparability.

All samples and associated results will be coded prior to being shipped from the site for analysis or storage. Samples will be tracked using a unique identifier that is assigned to the samples for the study. Results are stored in a secure database to ensure confidentiality.

If informed consent is provided by the subject, Amgen can do additional testing on remaining samples (ie, residual and back-up) to investigate and better understand the disease under study; ALL, the dose response and/or prediction of response to blinatumomab, characterize antibody response, and characterize aspects of the molecule (eg, mechanism of action/target, metabolites). Results from this analysis are to be documented and maintained, but are not necessarily reported as part of this study. Samples can be retained for up to 20 years.

Since the evaluations are not expected to benefit the subject directly or to alter the treatment course, the results of any exploratory studies are not placed in the subject's medical record and are not to be made available to the subject, members of the family, the personal physician, or other third parties, except as specified in the informed consent.

The subject retains the right to request that the sample material be destroyed by contacting the investigator. Following the request from the subject, the investigator is to provide the sponsor with the required study and subject number so that any remaining

Product: Blinatumomab
Protocol Number: 20130265

Date: 20 March 2019 Page 81 of 122

blood samples and any other components from the cells can be located and destroyed. Samples will be destroyed once all protocol-defined procedures are completed. However, information collected from samples prior to the request for destruction, will be retained by Amgen.

The sponsor is the exclusive owner of any data, discoveries, or derivative materials from the sample materials and is responsible for the destruction of the sample(s) at the request of the subject through the investigator, at the end of the storage period, or as appropriate (eg, the scientific rationale for experimentation with a certain sample type no longer justifies keeping the sample). If a commercial product is developed from this research project, the sponsor owns the commercial product. The subject has no commercial rights to such product and has no commercial rights to the data, information, discoveries, or derivative materials gained or produced from the sample. See Section 11.3 for subject confidentiality.

## 8. WITHDRAWAL FROM TREATMENT, PROCEDURES, AND STUDY

# 8.1 Subjects' Decision to Withdraw

Subjects have the right to withdraw from the study at any time and for any reason without prejudice to their future medical care by the physician or at the institution.

Subjects (or a legally acceptable representative) can decline to continue receiving investigational product and/or other protocol-required therapies or procedures at any time during the study but continue participation in the study. If this occurs, the investigator is to discuss with the subject the appropriate processes for discontinuation from investigational product or other protocol-required therapies and must discuss with the subject the options for continuation of the Schedule of Assessments (Table 6) and collection of data, including endpoints and adverse events. The investigator must document the change to the Schedule of Assessments (Table 6) and the level of follow-up that is agreed to by the subject (eg, in person, by telephone/mail, through family/friends, in correspondence/communication with other physicians, from review of the medical records).

Withdrawal of consent for a study means that the subject does not wish to receive further protocol-required therapies or procedures, and the subject does not wish to or is unable to continue further study participation. Subject data up to withdrawal of consent will be included in the analysis of the study, and where permitted, publically available data can be included after withdrawal of consent. The investigator is to discuss with the subject appropriate procedures for withdrawal from the study.

Date: 20 March 2019 Page 82 of 122

# 8.2 Investigator or Sponsor Decision to Withdraw or Terminate Subjects' Participation Prior to Study Completion

The investigator and/or sponsor can decide to withdraw a subject(s) from investigational product and/or other protocol-required therapies, protocol procedures, or the study as a whole at any time prior to study completion.

Subjects may be eligible for continued treatment with Amgen investigational product(s) and/or other protocol-required therapies by a separate protocol or as provided for by the local country's regulatory mechanism, based on parameters consistent with Section 12.1.

### 8.3 Reasons for Removal From Treatment

Reasons for removal from protocol-required investigational product(s) or procedural assessments include any of the following:

- Protocol-specified criteria:
  - Hematological or extramedullary relapse subsequent to achieving ≤ 5% blasts on protocol treatment
  - Failure to achieve bone marrow response defined as ≤ 5% blasts within
     2 complete treatment cycles
  - Investigator decision that a change of therapy (eg, immediate HSCT) is in the subject's best interest
- Subject request
- Safety concern (eg, due to toxicity of protocol-specified therapy or other adverse event)
- Decision by sponsor (other than subject request or safety concern)
- Death
- Lost to follow-up

## 8.4 Reasons for Removal From Study

Reasons for removal of a subject from the study are:

- Decision by sponsor
- Withdrawal of consent from study
- Death
- Lost to follow-up

As part of the study, sites may be asked to conduct searches of public records, such as those establishing survival status, if available, to obtain survival data for any subject for whom the survival status is not known.

**Product: Blinatumomab** 

Date: 20 March 2019 Page 83 of 122

#### 9. SAFETY DATA COLLECTION, RECORDING, AND REPORTING

#### 9.1 **Definition of Safety Events**

#### 9.1.1 **Definition of Adverse Events**

An adverse event is defined as any untoward medical occurrence in a clinical trial subject. The event does not necessarily have a causal relationship with study treatment. The investigator is responsible for ensuring that any adverse events observed by the investigator or reported by the subject are recorded in the subject's medical record.

The definition of adverse events includes worsening of a pre-existing medical condition. Worsening indicates that the pre-existing medical condition or underlying disease (eg, diabetes, migraine headaches, gout) has increased in severity, frequency, and/or duration, more than would be expected, and/or has an association with a significantly worse outcome than expected. A pre-existing condition that has not worsened more than anticipated (ie, more than usual fluctuation of disease) during the study or involves an intervention such as elective cosmetic surgery or a medical procedure while on study, is not considered an adverse event.

If the severity of an adverse event changes from the date of onset to the date of resolution, record as a single event with the worst severity on the Adverse Event Summary eCRF.

For situations when an adverse event or serious adverse event is due to ALL, report all known signs and symptoms. Death due to disease progression in the absence of signs and symptoms should be reported as the primary tumor type (eq. relapsed/refractory B-precursor ALL).

Note: The term "disease progression" should not be used to describe the adverse event.

An adverse device effect is any adverse event related to the use of a medical device. Adverse device effects include adverse events resulting from insufficient or inadequate instructions for use, adverse events resulting from any malfunction of the device, or adverse events resulting from use error or from intentional misuse of the device.

The investigator's clinical judgment is used to determine whether a subject is to be removed from treatment due to an adverse event. In the event a subject, or subject's legally acceptable representative requests to withdraw from protocol-required therapies or the study due to an adverse event, refer to Section 8.1 for additional instructions on the procedures recommended for safe withdrawal from protocol-required therapies or the study.

Date: 20 March 2019 Page 84 of 122

